10.3.12 Other events requiring reporting

10.3.12.1 Overdose

Use of durvalumab or tremelimumab in doses in excess of that specified in the protocol is considered to be an overdose. There is currently no specific treatment in the event of overdose of durvalumab or tremelimumab, and possible symptoms of overdose are not established.

- An overdose with associated AEs will be recorded as the AE diagnosis or symptoms in the relevant AE modules of the eCRF and in the Overdose eCRF module.
- An overdose without associated symptoms will only be reported in the Overdose eCRF module.

10.3.12.2 Pregnancy

All pregnancies and outcomes of pregnancy should be reported to the IND Sponsor and AstraZeneca.

Maternal exposure

If a patient becomes pregnant during the course of the study, the IPs should be discontinued immediately, and the pregnancy should be reported to the IND Sponsor and AstraZeneca.

Pregnancy itself is not regarded as an AE unless there is a suspicion that the IP under study may have interfered with the effectiveness of a contraceptive medication. Congenital abnormalities or birth defects and spontaneous miscarriages should be reported and handled as SAEs. Elective abortions without complications should not be handled as AEs. The outcome of all pregnancies (spontaneous miscarriage, elective termination, ectopic pregnancy, normal birth, or congenital abnormality) should be followed up and documented even if the patient was discontinued from the study.

Paternal exposure

Male patients should refrain from fathering a child or donating sperm during the study and for 180 days after the last dose of durvalumab + tremelimumab combination therapy or 90 days after the last dose of durvalumab monotherapy, whichever is the longer time period.

Pregnancy of the patient's partner is not considered to be an AE. However, the outcome of all pregnancies (spontaneous miscarriage, elective termination, ectopic pregnancy, normal birth, or congenital abnormality) occurring from the date of the first dose until 180 days after the last dose of durvalumab + tremelimumab combination therapy or 90 days after the last dose of durvalumab monotherapy, whichever is the longer time period should, if possible, be followed up and documented.

Where a report of pregnancy is received, prior to obtaining information about the pregnancy, the Investigator must obtain the consent of the patient's partner. Therefore, the local study team should adopt the generic ICF template in line with local procedures and submit it to the relevant Ethics Committees (ECs)/Institutional Review Boards (IRBs) prior to use.

10.3.12.3 Medication Error

For the purposes of this clinical study a medication error is an unintended failure or mistake in the treatment process for an AstraZeneca study drug that either causes harm to the patient or has the potential to cause harm to the patient.

A medication error is not lack of efficacy of the drug, but rather a human or process related failure while the drug is in control of the study site staff or patient.

Medication error includes situations where an error:

- occurred
- was identified and intercepted before the patient received the drug
- did not occur, but circumstances were recognized that could have led to an error

Examples of events to be reported in clinical studies as medication errors:

- Drug name confusion
- Dispensing error e.g. medication prepared incorrectly, even if it was not actually given to the patient
- Drug not administered as indicated, for example, wrong route or wrong site of administration
- Drug not taken as indicated e.g. tablet dissolved in water when it should be taken as a solid tablet
- Drug not stored as instructed e.g. kept in the fridge when it should be at room temperature
- Wrong patient received the medication (excluding IVRS/IWRS errors)
- Wrong drug administered to patient (excluding IVRS/IWRS errors)

Examples of events that **do not** require reporting as medication errors in clinical studies:

- Errors related to or resulting from IVRS/IWRS - including those which lead to one of the above listed events that would otherwise have been a medication error

- Patient accidentally missed drug dose(s) e.g. forgot to take medication
- Accidental overdose (will be captured as an overdose)
- Patient failed to return unused medication or empty packaging
- Errors related to background and rescue medication, or standard of care medication in open label studies, even if an AZ product

Medication errors are not regarded as AEs but AEs may occur as a consequence of the medication error.

If a medication error occurs in the course of the study, the IND Sponsor and AstraZeneca should be notified within 1 day i.e., immediately but **no later than 24 hours** of when he or she becomes aware of it.

11. STATISTICAL METHODS AND SAMPLE SIZE DETERMINATION

11.1 Description of analysis sets

11.1.1 Safety analysis set

Safety analysis set includes all patients who receive any study treatment including DEB-TACE or at least one dose of either durvalumab or tremelimumab.

11.1.2 Efficacy analysis set

Evaluable population for objective response includes all patients who receive DEB-TACE and both of durvalumab/tremelimumab, and have baseline scan with measurable disease, and either have at least one on treatment scan or die without any on treatment scans.

11.2 Methods of statistical analyses

11.2.1 Safety analyses

Safety will be summarized by the percentage of patients with AEs, by type and grade according to NCI CTCAE version 5.0 and attribution. The analysis will be based on safety analysis set.

11.2.2 Efficacy analyses

The primary endpoint is objective response. Objective response rate, defined as the percent of patients with at least one visit response of CR or PR via mRECIST and will be based on the Evaluable Population.

As a secondary endpoint, the response of non-target lesions will be described. Other secondary efficacy endpoints include duration of response, 6-month progression-free survival, and overall survival (OS). Duration of response is defined as date of having CR or PR to the date of progression per mRECIST among the patients who have CR or PR. Progression free survival will be defined as the time from the date of start of the treatment until the documentation of disease progression according to mRECIST or death due to any cause, whichever occurs first. Patients who have not progressed or died at the time of the analysis will be censored at the time of the latest date of assessment from their last evaluable mRECIST assessment. Kaplan-Meier

curves will be used to characterize PFS and OS, and 6-month PFS will be estimated from Kaplan-Meier.

11.2.3 Correlative analyses

Genomic sequencing library construction, whole genome/exome sequencing, whole transcriptome sequencing, microbial sequencing, neoepitope prediction, mutation burden, and bioinformatic analysis may be performed either at an on-campus laboratory or at an off-campus sequencing service. All the samples will be de-identified before sending to any laboratory for sequencing. The FASTQ files, BAM files and VCF files will be generated and analyzed. Other sequencing assays may be performed on a subset of samples according to specific requirements of collaboration projects. Genomic sequencing data will be stored and computations conducted using a JH IT managed subscription of Azure.

11.2.4 Safety run-in

To ensure that the combination is safe, the first six patients will be treated and observed for toxicity for 1 cycle before continuation with further accrual. If ≤ 1 limiting toxicity events occur in the first 6 patients, we will proceed with additional accrual to complete a total of 20 patients for the safety evaluation. If >1 limiting toxicity events occur among the first 6 patients, then three additional patients will be enrolled (i.e. a total of 9 patients). If ≤ 2 limiting toxicity events occur in the 9 patients, we will proceed with additional accrual to complete a total of 20 patients for the safety evaluation. If > 2 limiting toxicity events occur, we will pause the enrollment pending safety review.

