- Judgment by the investigator that the patient is unsuitable to participate in the study and the patient is unlikely to comply with study procedures, restrictions and requirements.

Investigational Product(s), Dose, and Mode of Administration:

Durvalumab 1500mg Q4W plus tremelimumab 300mg once via IV infusion, starting at 2 weeks after first DEB-TACE procedure. This will be followed by durvalumab monotherapy 1500 mg via IV infusion Q4W, until progression or unacceptable toxicity (maximum 13 doses/cycles).

Study Assessments and Criteria for Evaluation:

Safety Assessments:

To ensure that the combination is safe, the first six patients will be treated and observed for toxicity for 1 cycle before continuation with further accrual. If ≤ 1 limiting toxicity events occur in the first 6 patients, we will proceed with additional accrual to complete a total of 20 patients for the safety evaluation. If > 1 limiting toxicity events occur among the first 6 patients, then three additional patients will be enrolled (i.e. a total of 9 patients). If ≤ 2 limiting toxicity events occur in the 9 patients, we will proceed with additional accrual to complete a total of 20 patients for the safety assessment. If > 2 limiting toxicity events occur, we will pause the enrollment pending safety review.

Efficacy Assessments:

The primary endpoint is objective response using modified RECIST (mRECIST) criteria. The regimen would be considered of insufficient activity for further study if the response rate is 30%

or less, and the minimum required level of efficacy that would warrant further study with the proposed regimen is a 60% response rate.

Statistical Methods and Data Analysis:

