1.4.2.3 Durvalumab + tremelimumab

The safety of durvalumab + tremelimumab combination therapy is being evaluated in the ongoing dose escalation and dose expansion Study 006, in patients with NSCLC, and has so far shown a manageable safety and tolerability profile.

The potential risks with the combination of durvalumab + tremelimumab are similar to those for durvalumab and tremelimumab monotherapy. Emerging data from study 006 and from combinations of other agents in the same class indicate an increased frequency and/or severity of some of these potential immune-mediated toxicities.

In durvalumab+tremelimumab combination studies at the dose of durvalumab 20mg/kg and tremelimumab 1mg/kg AEs (all grades) reported very commonly ($\geq 10\%$ of patients) are fatigue, diarrhoea, nausea, dyspnea, decreased appetite, pruritus, vomiting, anaemia, constipation, cough, abdominal pain, pyrexia, back pain, hyponatremia and rash.

Approximately 13% of patients experienced an AE that resulted in permanent discontinuation of study drug and approximately 13% of patients experienced an SAE that was considered to be related to durvalumab and tremelimumab by the study investigator.

A detailed summary of durvalumab + tremelimumab combination AE data can be found in the current version of the durvalumab IB.

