6.2 Dosage and administration

6.3 Definition of Unacceptable Toxicity

The combination of tremelimumab and durvalumab has been previously tested in a dose-escalation study performed by AstraZeneca employing dose ranges of 1-10mg/kg q4weeks (tremelimumab) and 10-20mg/kg q2-4weeks (durvalumab). Patients treated in the 20 mg/kg durvalumab + 1 mg/kg tremelimumab group had the fewest AEs, Grade ≥ 3 AEs, SAEs, and treatment discontinuations due to AEs, but still showed strong evidence of clinical activity. This cohort had a lower number of treatment-related Grade ≥ 3 AEs or treatment related SAEs. No dose-limiting toxicities were reported. This is the dose level we will be administering for this study. Also, PK analysis indicated only minor impact of body weight (WT) on PK of both agents so to minimize errors and for ease of use the company have moved to a fixed-dose schedule of 1500 mg Q4W durvalumab (equivalent to 20 mg/kg Q4W) and 75 mg Q4W tremelimumab (equivalent to 1mg/kg Q4W).

Unacceptable toxicities will be evaluated from the time of first administration of durvalumab or tremelimumab until the Week 6 evaluation (prior to the second dose of durvalumab). Patients who do not remain on the study through the completion of this safety run-in period for reasons other than DLT will be replaced with another patient (see **Section 11.2.4** for details of safety run-in). Grading of unacceptable toxicities will follow the guidelines provided in the Common Terminology Criteria for Adverse Events (CTCAE) version 5.0.

An unacceptable toxicity will be defined as any toxicity occurring during the study that meets the criteria below. Toxicity that is clearly and directly related to the primary disease or to another etiology is excluded from this definition. The following will be unacceptable toxicities:

- Any Grade 4 irAE
- Any \geq Grade 3 colitis
- Any Grade 3 or 4 non-infectious pneumonitis irrespective of duration
- Any Grade 2 pneumonitis that does not resolve to \leq Grade 1 within 3 days of the initiation of maximal supportive care
- Any Grade 3 irAE, excluding colitis or pneumonitis, that does not downgrade to Grade 2 within 3 days after onset of the event despite optimal medical management including systemic corticosteroids or does not downgrade to \leq Grade 1 or baseline within 14 days
- Liver transaminase elevation $> 8 \times$ ULN or total bilirubin $> 5 \times$ ULN (other than the 1st week following DEB-TACE)

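### The safety run-in expands from 6 to 9 patients after any count above 1, including counts of 3 or more at which the 9-patient criterion has already failed

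*Combined protocol and SAP*

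**What the plan says.** Section 11.2.4 (Safety run-in) sets a two-step rule, and the synopsis repeats it under Safety Assessments.

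- **First look:** "the first six patients will be treated and observed for toxicity for 1 cycle before continuation with further accrual".
- **Go at six:** "If ≤ 1 limiting toxicity events occur in the first 6 patients, we will proceed with additional accrual".
- **Expand:** "If >1 limiting toxicity events occur among the first 6 patients, then three additional patients will be enrolled (i.e. a total of 9 patients").
- **Go at nine:** "If ≤ 2 limiting toxicity events occur in the 9 patients, we will proceed with additional accrual".
- **Pause:** "If > 2 limiting toxicity events occur, we will pause the enrollment pending safety review".

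The expansion sentence has a lower limit and no upper one, so it covers 2, 3, 4 or more events. The pause sentence names neither a denominator nor a time point. Section 6.3 adds that patients who leave the run-in for "reasons other than DLT will be replaced with another patient". It provides no replacement for those who leave because of a limiting toxicity.

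**The concern.** Expanding a run-in makes sense when the result at the first look is borderline and a few more patients could settle it. Here the expansion also applies to results that are not borderline. Once three events have been seen in six patients, a criterion of at most two in nine cannot be met.

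What is at stake depends on how the pause sentence is read.

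- **It applies only at nine patients.** Its position, directly after the 9-patient criterion, suggests this. Up to three more patients then receive the combination after the plan's own limit has been exceeded, and their outcomes cannot alter go or pause.
- **It applies at any time.** Nobody extra is exposed, but for 3 or more events in six the plan gives opposite instructions and does not say which one governs.

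Either way the rule fails at the result where it matters most. Section 1.3.5.1 states that no clinical data existed for durvalumab 1500 mg with a single 300 mg tremelimumab dose when the protocol was drafted.

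**Working it through.** The plan states no operating characteristic for the run-in, so there is no figure of its own to reproduce.

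**Step 1: the logic.** Let x be the number of events in the first six patients and y the number in the next three. The nine include the first six, and nothing in sections 6.3 or 11.2.4 removes an event once it is counted, so the total is x + y ≥ x.

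| Events in first six | Instruction as written | Can 2 or fewer in nine still be met? |
|---|---|---|
| 0 or 1 | Continue accrual | Not needed |
| 2 | Enrol three more | Yes, if y = 0 |
| 3 or more | Enrol three more | No |

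Expansion can affect the decision only when x = 2. This holds whatever the toxicity rate.

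**Step 2: how often it would arise.** The documents give no expected limiting-toxicity rate. I assume true rates p from 10% to 50%, independent patients and at most one event per patient, so X ~ Binomial(6, p). The 13% row uses the only rate in the plan that comes near. Section 1.4.2.3 reports that "approximately 13% of patients experienced an SAE that was considered to be related to durvalumab and tremelimumab". That is a different endpoint, at tremelimumab 1 mg/kg, so it serves only as a low reference point.

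Formulas, on the reading that the pause applies only at nine patients:

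- Expansions that cannot succeed: P(X ≥ 3)
- Their share of all expansions: P(X ≥ 3) / P(X ≥ 2)
- Expected extra patients in such expansions: 3 × P(X ≥ 3)
- Probability of proceeding: P(X ≤ 1) + P(X = 2) × (1 − p)³

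Worked example at p = 0.20:

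- P(X = 0) = 0.8⁶ = 0.2621
- P(X = 1) = 6 × 0.2 × 0.8⁵ = 0.3932
- P(X = 2) = 15 × 0.2² × 0.8⁴ = 0.2458
- P(X ≥ 3) = 1 − 0.9011 = 0.0989
- Share = 0.0989 / 0.3446 = 0.287
- Extra patients = 3 × 0.0989 = 0.30
- Proceed = 0.6554 + 0.2458 × 0.512 = 0.781

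| Assumed rate | P(X = 2) | P(X ≥ 3) | Share of expansions that cannot succeed | Expected extra patients | P(proceed) |
|---|---|---|---|---|---|
| 10% | 9.8% | 1.6% | 14% | 0.05 | 95.7% |
| 13% | 14.5% | 3.2% | 18% | 0.10 | 91.8% |
| 20% | 24.6% | 9.9% | 29% | 0.30 | 78.1% |
| 30% | 32.4% | 25.6% | 44% | 0.77 | 53.1% |
| 40% | 31.1% | 45.6% | 59% | 1.37 | 30.0% |
| 50% | 23.4% | 65.6% | 74% | 1.97 | 13.9% |

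**Step 3: effect of an upper limit.** P(proceed) has no term for X ≥ 3, so it is the same with and without the limit. Expected run-in size changes from 6 + 3 × P(X ≥ 2) to 6 + 3 × P(X = 2):

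| Assumed rate | As written | With the limit |
|---|---|---|
| 10% | 6.34 | 6.30 |
| 20% | 7.03 | 6.74 |
| 30% | 7.74 | 6.97 |
| 40% | 8.30 | 6.93 |
| 50% | 8.67 | 6.70 |

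**The case against.** The strongest reply is that the pause sentence carries no denominator while the sentence before it does, so it can be read as a standing limit. The expansion branch then operates as exactly 2, and no extra patient is exposed. That reading is available. It does not repair the text, because the expansion sentence still instructs the opposite for 3 or more events and nothing ranks the two.

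Other points, and what stands of each:

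- **The extra patients would inform the safety review.** Three events in nine does tell a reviewer something different from three in six. The claim is therefore limited to the go/pause decision, which they cannot change. The plan does not give this as a reason to enrol them.
- **Other oversight exists.** Section 10.3.11 requires serious events to be reported within 24 hours, section 13.1 has the team review each patient, and section 14.1 describes company monitoring. Accrual also stops after six patients for one cycle of observation. These make mechanical enrolment after three or more events less likely, but none of them sets a numerical limit.
- **The larger figures rest on assumed rates.** This is correct. Nothing in the documents supports 40% or 50%, the 13% reference gives only 0.10 expected patients, and section 6.3 reports no dose-limiting toxicities in the 1 mg/kg tremelimumab cohort. That dose is lower than the 300 mg given here, so neither anchor settles the rate.
- **Section 4.4 replaces patients who become unsuitable through medical complications.** It does not say that an event already counted is dropped, and section 6.3 is the provision specific to the run-in.
- **Efficacy is untouched.** This also stands, and it limits the weight of the point.

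**Conclusion.** The concern holds. That 3 or more events in six rule out at most 2 in nine follows from the plan's own wording and needs no assumed rate. The consequence is either up to three further patients treated with no bearing on the go/pause decision, or two conflicting instructions.

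The practical weight is modest. If the pause applies only at nine patients, expected extra exposure runs from 0.05 patients per trial at an assumed 10% rate to 1.97 at 50%. If the pause is a standing limit, it is zero and the problem is one of wording. The figures assume independent patients with at most one event each. The rule counts events, so if one patient can contribute several, three events would be reached at least as often. The two-stage efficacy design and the primary analysis are unaffected.

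**What to change.** In section 11.2.4 and in the synopsis, replace the open-ended expansion with a bounded one, for example:

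> Three further patients (nine in all) are added only when the first six have had exactly 2 limiting toxicity events. Enrolment is paused for safety review once the cumulative count exceeds 2, at any point in the six or the nine.

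This keeps the plan's own limit and its counting of events. Counting patients with an event instead is a separate choice that would make the rule less conservative, and it is not proposed here.

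The cost is one sentence in each of two places. The final go/pause decision does not change, because 3 or more events in six always means more than 2 in nine, and run-in exposure can only fall. The document is version 11.0 and does not say whether the run-in is complete. If it is, the change only corrects the record.

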11.3 Determination of sample size

The standard of care treatment with DEB-TACE results in a objective response rate (ORR) of 30%. The regimen would be considered of insufficient activity for further study if the ORR is 30% or less, and the minimum required level of efficacy that would warrant further study with the proposed regimen is a 60% response rate. An optimal Simon two-stage design is planned. A total of 8 patients will be entered in the first stage. If ≤ 2 subjects respond, the treatment will be terminated and we will conclude the regimen is ineffective. If ≥ 3 subjects respond, then additional 12 patients will be studied. If a total of 8 or fewer subjects respond in stage one and two combined, the regimen is considered ineffective. If a total of 9 or more respond, we conclude the regimen is promising and warrants further study. The maximum sample size will be 20 evaluable patients. To account for 10% unevaluable patients who do not receive durvalumab/tremelimumab following DEB-TACE, or do not have any on treatment scans for reasons other than death, we plan to enroll 22 patients.

This design provides 90% power to detect a 30% absolute increase in ORR, from 30% to 60%, with one-sided type I error 0.1. The chance of stopping early for lack of efficacy at the interim analysis is 0.55, if the response rate is 30%.

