4.4 Replacement of patients

If a patient is lost to follow up after the first DEB-TACE or deemed not appropriate for further treatment with durvalumab or tremelimumab due to medical complications, patients will be replaced. If patients do not have treatment scans for reasons other than death, patients will be replaced.

[figure not shown]
[figure not shown]
[figure not shown]

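### Section 11.3 caps the design at 20 evaluable patients but plans to enrol 22, and no rule says which 20 decide the primary outcome if 21 or 22 qualify

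*Combined protocol and SAP*

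**What the plan says.** Section 11.3 sets out the design: "An optimal Simon two-stage design is planned", with a null response rate of 30% and a target of 60%. On stage 1 it says "A total of 8 patients will be entered in the first stage"; the trial stops if 2 or fewer respond. Otherwise 12 more are studied, and the regimen is called promising if 9 or more respond in total. No other final cut-off is given. The same section says "The maximum sample size will be 20 evaluable patients" and then, to allow for 10% unevaluable patients, "we plan to enroll 22 patients". It claims one-sided type I error 0.1, 90% power and a 0.55 chance of stopping early under the null. The synopsis repeats all of this.

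Section 11.1.2 defines the primary set without a number: "Evaluable population for objective response includes all patients who receive DEB-TACE and both of durvalumab/tremelimumab", subject to a baseline scan with measurable disease and either an on-treatment scan or death before one. Section 11.2.2 bases the primary response rate on that set.

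Section 4.4 adds replacement: "If patients do not have treatment scans for reasons other than death, patients will be replaced". Patients lost after the first DEB-TACE, or medically unsuitable for the study drugs, are replaced too. It does not say whether replacements come out of the 22 or on top of it.

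**The concern.** The cap and the set definition agree only if no more than 20 patients turn out evaluable. If 21 or 22 qualify, section 11.1.2 puts them all in the primary set, while 11.3 allows 20 in the design and gives one cut-off, which belongs to 20. The analyst must then either count everyone against 9, or leave out one or two qualifying patients by a rule that the plan does not contain.

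This rule is the trial's primary go/no-go decision, and a single responder can settle it. The study is open-label, and section 13.1 has the principal investigator review each patient's response data, so a choice made at that point would be made with responses known. The design has almost no slack to absorb it, because its exact type I error already sits at the limit.

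**Working it through.** **Inputs.** From section 11.3: p0 = 0.30; p1 = 0.60; stage 1 size 8, continue with 3 or more responders; 12 more patients; final cut-off 9; 22 enrolled; 10% unevaluable. Assumed here: stage 1 is exactly 8 evaluable patients whatever the final number N.

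**Formula.** P(promising) = sum over x = 3 to 8 of P(Bin(8, p) = x) × P(Bin(N − 8, p) ≥ 9 − x). Early stopping is P(Bin(8, p) ≤ 2).

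**Step 1: reproduce the plan (N = 20, p = 0.30).**

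| Stage 1 responders x | P(x of 8) | P(at least 9 − x of 12) | Product |
|---|---|---|---|
| 3 | 0.25412 | 0.11785 | 0.02995 |
| 4 | 0.13614 | 0.27634 | 0.03762 |
| 5 | 0.04668 | 0.50748 | 0.02369 |
| 6 | 0.01000 | 0.74718 | 0.00747 |
| 7 | 0.00122 | 0.91497 | 0.00112 |
| 8 | 0.00007 | 0.98616 | 0.00006 |

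The products sum to 0.0999. With p = 0.60 the same sum gives power 0.912. Early stopping under the null is 0.552. A search over all two-stage designs up to 30 patients confirms that this is the Simon optimum for these error limits. The plan's figures therefore reproduce.

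**Step 2: keep the cut-off at 9 and let N vary.**

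| Evaluable N | Type I error | Power |
|---|---|---|
| 18 | 0.056 | 0.848 |
| 19 | 0.077 | 0.887 |
| 20 | 0.0999 | 0.912 |
| 21 | 0.125 | 0.928 |
| 22 | 0.152 | 0.938 |

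**Step 3: how often N differs from 20.** Assume 22 are enrolled and each is independently unevaluable with probability 0.10. From Bin(22, 0.9): P(21) = 0.241 and P(22) = 0.098, together 0.339; P(20) = 0.281; P(fewer than 20) = 0.380. The chance of 21 or 22 depends on the assumed rate: it is 0.70 at 5% unevaluable and 0.14 at 15%.

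**Step 4: average type I error, all qualifying patients counted against 9.**

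- No replacement: weighting the exact type I error at each N by Bin(22, 0.9) gives 0.097.
- Shortfalls replaced up to 20, as section 4.4 allows: P(20 or fewer before replacement) = 0.281 + 0.380 = 0.661, so 0.661 × 0.0999 + 0.241 × 0.1253 + 0.098 × 0.1521 = 0.0660 + 0.0302 + 0.0149 = 0.111.

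**Step 5: possible remedies.**

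- Decide on the first 20 evaluable patients: type I error 0.0999 and power 0.912, as in step 1.
- Count everyone and require 10 responders: type I error 0.061 and power 0.8885 at N = 21; type I error 0.081 and power 0.912 at N = 22. At 21 the power is below the stated 90%.

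**The case against.** The best reply is that the plan already limits the decision to 20. Section 11.3 says so in the passage that holds the decision rule, and the 22 appears only as an allowance for reaching 20. The synopsis gives a study population of 20, the safety run-in accrues to 20, and the matched control group has 20. On that reading, 0.125 and 0.152 describe a trial outside the design. This stands against one inference that a reader might draw, that the stated type I error of 0.1 is wrong. It is right for the design at N = 20. What the cap does not do is say which 20 count, and section 11.1.2 still admits every patient who qualifies.

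A second reply is that falling short of 20 (0.38) is more probable than exceeding it (0.34), and that the fixed rule averages 0.097 over both. The numbers are correct, and they rule out calling an overrun likely. But the 0.097 leaves section 4.4 out. Replacement removes the small trials that pull the average down and leaves the large ones; the average is then 0.111.

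A third reply is that no section provides for dropping evaluable patients. That is so, and nothing in the documents suggests that anyone intends to choose patients by response. The point is only that, with 21 or 22 qualifying, the cap cannot be honoured without leaving someone out, and the plan gives no rule for doing it.

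**Conclusion.** The concern holds as an unreconciled pair of rules, not as an error in the stated operating characteristics. Counting all qualifying patients, as 11.1.2 and 11.2.2 direct, against the only cut-off in 11.3 exceeds the stated type I error whenever 21 or 22 qualify: 0.125 or 0.152 against 0.10.

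It would be too strong to say that the cut-off of 9 is valid only for exactly 20 patients. With fewer than 20, type I error stays below 0.10 and the cost is power alone.

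The 0.34 probability and both averages rest on independent 10% unevaluability among 22 enrolled; the 0.111 also assumes replacement only up to 20. The type I error at each N assumes a stage 1 of exactly 8 evaluable patients. The effect is moderate, but it bears on the primary decision and should be settled before the final analysis.

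**What to change.** Add to section 11.3, with a matching sentence in 11.1.2 and the synopsis: the stage 1 and final go/no-go decisions use the first 8 and the first 20 evaluable patients in order of enrolment; the response rate and its confidence interval in all evaluable patients are reported as supplementary.

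This keeps type I error at 0.0999 and power at 0.912 however many of the 22 qualify, provided at least 20 do. Raising the cut-off to 10 for larger numbers is not recommended, because at 21 patients it loses the stated power.

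The cost is one sentence in each place, with no extra patients and no change to any procedure.
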